2.6.2.3 Number of Gd-enhancing lesions per scan

The null hypothesis is that there is no difference in the number of Gd-lesion per scan between ofatumumab 20mg sc and teriflunomide 14 mg po

- Superiority of ofatumumab 20mg sc over teriflunomide 14 mg po will be concluded if there are fewer Gd-lesions per scan (estimated rate ratio from a negative binomial model < 1) in patients treated with ofatumumab compared with teriflunomide and the observed p-value for the between-treatment comparison is less than the two-sided significance level of 0.05. The multiplicity adjustment explained in [Section 2.5.3](#) applies.

Confirmatory analysis of the number of Gd-lesions per scan: The confirmatory analysis of the number of Gd-lesions per MRI-scan will be done based on the FAS using a negative binomial regression model with log-link. The total number of Gd-enhancing T1 lesions (derived as in [Section 2.6.1.3](#)) will be used as the response variable, and the natural log of the number of MRI-scans (derived as in [Section 2.6.1.3](#)) will serve as the offset variable to adjust for the different number of MRI-scans between patients related to the flexible follow-up time in this study. The model will include treatment and region (factors), and age, and number of Gd-enhancing T1 lesions at baseline as continuous covariates.

The number of Gd-lesions per scan will be estimated by treatment with 95% confidence interval. The between treatment effect will be calculated as rate-ratio with 95% confidence interval and p-value. In addition the relative reduction in the number of Gd-lesion per scan will be computed as one (1) minus the rate-ratio and expressed as a percentage.

Supportive analysis: The number of Gd-lesions will be summarized descriptively by visit-window and treatment group.

2.6.2.4 Annualized rate of new or enlarging T2 lesions

The null hypothesis is that there is no difference in the number of new or enlarging T2 lesions between ofatumumab 20mg sc and teriflunomide 14 mg po

- Superiority of ofatumumab 20mg sc over teriflunomide 14 mg po will be concluded if there are fewer new or enlarging T2 lesions (estimated rate ratio from a negative binomial model < 1) in patients treated with ofatumumab compared with teriflunomide and the observed p-value for the between-treatment comparison is less than the two-sided significance level of 0.05. The multiplicity adjustment explained in [Section 2.5.3](#) applies.

Confirmatory analysis of the Annualized rate of new or enlarging T2 lesions: The confirmatory analysis of the annualized rate of new or enlarging T2 lesions will be done based on the FAS using a negative binomial regression model with log-link. The number of new or enlarging T2 lesions on the last available MRI scan relative to baseline (derived as in [Section](#)

[2.6.1.4](#)) will be used as the response variable, and the natural log of the time (in years) of the MRI assessment from the baseline scan (as defined in [Section 2.6.1.4](#)) will serve as the offset variable to adjust for the various lengths of follow-up times between patients in this study. The model will include treatment and region (factors), and age, and baseline volume of T2 lesions as continuous covariates.

The number of new or enlarging T2 lesions per year will be estimated by treatment with 95% confidence interval. The between treatment effect will be calculated as rate-ratio with 95% confidence interval and p-value. In addition the relative reduction in the number new or enlarging T2 lesions per year will be computed as one (1) minus the rate-ratio and expressed as a percentage.

Supportive analysis: The number of new or enlarging T2 lesions collected at each visit will be summarized descriptively by treatment group.

The number of new or enlarging T2 lesions are a cumulative measure of disease activity. Since the number of new or enlarging T2 lesion is assessed relative to the MRI scan collected at screening (i.e. well before the start of study medication intake), it is expected that this analysis underestimates the true treatment effect. Therefore, a supportive analysis will be performed based on the new or enlarging T2 lesions between the Month 12 scan and the End of Study scan.

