2.3.3 MS baseline disease characteristics

MS baseline characteristics, MS disease history and MS medication history will be summarized by treatment group for the FAS in the individual study reports but also side-by-side for the two studies in the combined report to evaluate poolability of the two ASCLEPIOS trials.

MS baseline characteristics include baseline EDSS, 9HPT, T25FW, SDMT, and key MRI parameters (e.g., number of Gd-enhancing T1 lesions, T2 lesion volume, and normalized brain volume).

MS disease history includes duration of MS since diagnosis (years), duration of MS since first symptom (years), number of relapses in the last 12 months prior to screening, number of relapses in the 12 to 24 months prior to screening, type of MS at study entry (i.e., RRMS or SPMS), time since onset of SPMS, and time since onset of most recent relapse (months) prior to screening.

Duration of MS since diagnosis (years) will be derived $[(\text{first dose date} - \text{MS diagnosis start date} + 1)/365.25]$; duration of MS since first symptom (years) will be derived as $[(\text{first dose date} - \text{first MS symptom date} + 1)/365.25]$; time since onset of SPMS (years) will be derived as $[(\text{first dose date} - \text{conversion to SPMS date} + 1)/365.25]$; and time since onset of most recent relapse (months) will be derived as $[(\text{first dose date} - \text{most recent relapse onset date} + 1)/(365.25/12)]$. In these calculations, partial dates if any will be imputed according to the rules specified in [Section 5.1.3.3](#).

MS medication history of previous disease-modifying drugs (coded by WHO drug dictionary) will be summarized by preferred term (PT) and treatment group. The number and proportion of treatment-naïve patients (i.e., patients who have not been treated with any disease-modifying drug before study enrolment) will also be presented.

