2.5.2 Statistical hypothesis, model, and method of analysis

The null hypothesis is that there is no difference in the ARR between ofatumumab 20mg sc once monthly and teriflunomide 14 mg po once daily in reducing the frequency of confirmed MS relapses as measured by ARR. The alternative hypothesis is that there is a difference between the two treatment groups.

Superiority of ofatumumab 20mg sc over teriflunomide 14 mg po will be concluded if the observed ARR on ofatumumab 20mg sc is lower than on teriflunomide 14 mg po and if the null hypothesis can be rejected at the two-sided significance level of 0.05.

The null hypothesis will be tested based on the FAS, using a negative binomial regression model with log-link, treatment and region as factors, number of relapses in previous year, baseline

[figure not shown]
EDSS, baseline number of T1 Gd-enhancing lesions and the patient's age at baseline as covariates. In the analysis, the response variable is the number of confirmed relapses observed from each patient and the patient's time in study (natural log of time in years) is used as an offset variable to adjust for the varying lengths of patient's time in the study. The adjusted ARR (i.e., model-based estimate adjusted for covariates) for each treatment and the corresponding 95% confidence interval, and ARR ratio (also expressed as percentage reduction relative to control group) along with the 95% confidence interval for the ARR ratio and the corresponding p-value will be obtained.

The definition of Region is intended to correspond to that used for the stratification of the randomization. However, the definition of Region may be modified if that is indicated based on statistical criteria (e.g. non-convergence of models).

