2.6.2.5 Neurofilament light chain (NfL)

The null hypothesis is that there is no difference in NfL between ofatumumab 20 mg sc and teriflunomide 14 mg po by month 3.

- Superiority of ofatumumab 20 mg sc over teriflunomide 14 mg po will be concluded if NfL levels are already lower at month 3 in patients treated with ofatumumab compared with teriflunomide and the observed p-value for the between-treatment comparison is less than the two-sided significance level of 0.05. The multiplicity adjustment explained in [Section 2.5.3](#) applies.
- **Confirmatory analysis of NfL:** The NfL concentration (geometric mean concentration) will be estimated by treatment and time point with 95% confidence intervals using a repeated measures model on the basis of all evaluable log-transformed NfL values (the natural log will be used). The response variable is the log-transformed values of the NfL level as the NfL level is expected to follow log-normal distribution. The exponentiated treatment differences are the geometric mean ratios (GMR) which will be reported by visit window with 95% confidence intervals and p-values. The statistical hypothesis test will be based on the treatment contrast and p-value obtained at month 3. An unstructured covariance matrix will be used. The model will include treatment, region and visit window as factors, and age, number of Gd-enhancing lesions at baseline, baseline T2 lesion volume and the log-transformed NfL baseline concentration as continuous adjustments. The model will also include a treatment-by-timepoint interaction to allow the treatment effect to vary over time. The treatment effect of ofatumumab versus teriflunomide will be visualized in a line plot with 95% confidence intervals.

Supportive analysis: If ofatumumab significantly reduces NfL as compared with teriflunomide, the following additional analyses will be performed. In all patients (FAS), and additionally in the subgroup of newly diagnosed (within 3 years prior to the screening visit) and treatment-

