2.6.2.6 Brain volume loss

The null hypothesis is that there is no difference in brain volume change between ofatumumab 20mg sc and teriflunomide 14 mg po

- Superiority of ofatumumab 20mg sc over teriflunomide 14 mg po will be concluded if there is less brain volume loss (positive difference in slope from the random coefficient model) in patients treated with ofatumumab compared with teriflunomide and the observed p-value for the between-treatment comparison is less than the two-sided significance level of 0.05. The multiplicity adjustment explained in [Section 2.5.3](#) applies.

Confirmatory analysis of brain volume loss: The percentage change from baseline in brain volume will be estimated on the basis of all scheduled scans up to the last available MRI scan that evaluated percentage brain volume change relative to baseline. A random coefficients model will be used as main analysis for this endpoint in order to adjust for the various length of follow-up time in this study. Brain volume change was approximately linear over time and approximately normally distributed in 3 independent studies of the fingolimod phase 3 program. The random coefficients model will include treatment, region as fixed effects (factors), and time, number of Gd-enhancing lesions at baseline, baseline T2 volume, and normalized brain volume at baseline as continuous covariates and treatment by time interaction. Time as a continuous covariate allows for estimation of different slopes and intercepts among treatment groups. The model will also contain random terms to account for deviations about the population slope and intercept. The statistical test will address the question whether there is a difference in the slope of brain volume change by treatment group. The annual rate of percent change from baseline in brain volume is approximates as the population slope within the treatment group. Since the random coefficients model allows for the estimation of different slopes and intercepts among the treatment groups, differences between treatments at any time can be summarized using this model. Model estimates of percentage brain volume change at Months 12 and 24 will be provided by treatment with corresponding 95% confidence interval. Treatment differences will be estimated at the same time points with confidence interval and a p-value for the test of a difference in slope.

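### The T2-lesion model leaves out the baseline Gd-enhancing lesion count that the ARR, NfL and other key-secondary MRI models use, so the lesion rate ratio may be estimated less precisely than the data allow

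*SAP*

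**What the plan says.** SAP 2.6.2.4 specifies a negative binomial regression for the number of new or enlarging T2 lesions on the last available scan, with log time from the screening scan as offset. On covariates, the "model will include treatment and region (factors), and age, and baseline volume of T2 lesions as continuous covariates". Protocol 9.5.1.1.4 gives the same list.

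The related models treat the baseline Gd count differently:

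- Primary ARR model (SAP 2.5.2): "EDSS, baseline number of T1 Gd-enhancing lesions and" age are among the covariates.
- Gd lesions per scan (SAP 2.6.2.3): age "and number of Gd-enhancing T1 lesions at baseline as continuous covariates".
- NfL (SAP 2.6.2.5): "age, number of Gd-enhancing lesions at baseline, baseline T2 lesion volume and the log-transformed NfL baseline concentration as continuous adjustments".
- Brain volume loss (SAP 2.6.2.6): "number of Gd-enhancing lesions at baseline, baseline T2 volume, and normalized brain volume at baseline as continuous covariates".
- NEDA-4 logistic model (SAP 2.7.2): baseline Gd count is included.

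SAP 2.3.3 lists "number of Gd-enhancing T1 lesions, T2 lesion volume, and normalized brain volume" among the baseline MRI characteristics to be summarised, so the value is in the analysis data. Neither document explains its absence from the T2 model or plans a sensitivity analysis that adds it.

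**The concern.** Gd enhancement marks current inflammatory activity. The protocol itself uses Gd-enhancing lesions to define an active population (Protocol 3.2), and both documents describe the T2 count as a cumulative measure of disease activity. A baseline activity marker is therefore a natural candidate predictor of later new T2 lesions. Collinearity with T2 volume is unlikely to be the reason for leaving it out, because the NfL and brain-volume models use both together.

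What is at stake is precision. In a negative binomial model with large dispersion, most of the variance of the log rate ratio is between-patient variability. A prognostic baseline covariate reduces that part. Under a log link, adjusting for a baseline covariate leaves the targeted rate ratio essentially unchanged.

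**Working it through.** **Inputs.** Mean counts over 1.5 years of 2.1 (teriflunomide) and 0.42 (ofatumumab), dispersion κ = 3.1, 20% dropout (Protocol 9.8.6). 450 patients are randomised per arm (Protocol 9.8), so 450 × 0.8 = 360 per arm have scans. The variance form is that of Protocol Appendix 5.

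**Reproducing the plan's figure.**
n per arm = (1.960 + 1.282)² × (1/2.1 + 1/0.42 + 2 × 3.1) / (ln 5)² = 10.507 × 9.057 / 2.590 = 36.74.
That rounds up to 37 per arm, or 74 evaluable. Then 37/0.8 = 46.25, rounded up to 47 per arm, or 94 randomised. Protocol 9.8.6 is reproduced exactly. SAP 3.1.3 gives 66 and 84, which the same inputs do not reproduce. They appear if the 1.5 years is applied a second time to counts that already cover 1.5 years (3.15 vs 0.63 gives 32.88, so 33 per arm). With 900 randomised this has no practical effect here.

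**Precision at the trial's size.**
SE = √[(1/2.1 + 1/0.42 + 2κ)/360] = √[(2.857 + 2κ)/360].
At κ = 3.1 the dispersion term is 6.2 of 9.057, or 68% of the variance.

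| Assumed fall in κ | κ | SE | Log-scale interval narrower by | Variance lower by | 95% CI around 0.20 |
|---|---|---|---|---|---|
| 0% | 3.10 | 0.1586 | 0% | 0% | 0.147 to 0.273 |
| 10% | 2.79 | 0.1531 | 3.5% | 6.8% | 0.148 to 0.270 |
| 20% | 2.48 | 0.1474 | 7.1% | 13.7% | 0.150 to 0.267 |
| 30% | 2.17 | 0.1414 | 10.9% | 20.5% | 0.152 to 0.264 |

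The falls in κ are assumptions. Neither document says how well baseline Gd count predicts new T2 lesions once age, region and T2 volume are in the model.

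**Simulation.** This used 150 runs per setting, 360 per arm and an assumed skewed Gd count, with no other covariates. The SE of the log rate ratio without and with the covariate was:

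- No effect of Gd count: 0.159 and 0.159.
- Weak effect (0.05 on the log rate per lesion): 0.158 and 0.158.
- Moderate effect (0.10): 0.150 and 0.149 model-based; 0.149 and 0.143 empirical.
- Strong effect (0.15): 0.135 and 0.129 model-based; 0.164 and 0.136 empirical.

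A gain therefore appears only if the association is real, and it is small unless the association is fairly strong.

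**Power, main test.** ln 5/0.1586 − 1.96 = 8.19, so power exceeds 99.99% with or without the covariate.

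**Power, Month 12 to EOS.** Assume only 0.5 year between scans, giving means of 0.7 and 0.14. The bracket is 1/0.7 + 1/0.14 + 6.2 = 14.77.

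- 360 per arm: SE 0.203, power >99.99%.
- 200 per arm: SE 0.272, power >99.9%.
- 100 per arm: SE 0.384, power about 98.7%.

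Dispersion is 6.2/14.77 = 42% of the variance here, so the same 10%, 20% and 30% falls narrow the interval by only 2.1%, 4.3% and 6.5%.

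**The case against.** The strongest reply is that this is a legitimate prespecified choice. The two lesion-count models follow one pattern: each adjusts for the baseline measure of its own lesion type, Gd count for Gd lesions and T2 volume for T2 lesions. Protocol and SAP agree, the main test is heavily overpowered, and nothing here creates bias or inflates type I error. All of that stands. The point is an available improvement, not an error.

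Several stronger readings are tempting, and the documents do not support them:

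- *The rate ratio is less precise than it could be.* This is conditional. If Gd count adds nothing beyond age, region and T2 volume, the gain is zero.
- *Every other MRI model adjusts for Gd count.* This is true of the other key-secondary MRI models only. The rank ANCOVA for T2 lesion volume (SAP 2.7.2) also omits it.
- *The covariate is needed for power in the Month 12 to EOS analysis.* At the planned 80% reduction it is not, as shown above.
- *The adjustment is free.* Patients without a baseline Gd count would drop out, because neither document describes imputing baseline covariates. A loss of 6.8% of patients would cancel the gain from a 10% fall in dispersion.
- *The covariate belongs in the NfL analyses too.* The T2 test in SAP 2.6.2.5 contrasts high with low baseline NfL within the teriflunomide group, and NfL category is not randomised. Adding Gd count changes the question from whether NfL predicts new lesions to whether it predicts beyond Gd. The ARR and brain-volume versions already adjust for Gd through their parent models, so there is an inconsistency to consider, but resolving it means choosing what to estimate.

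**Conclusion.** The point holds as an optional efficiency improvement. The baseline Gd count is missing from the confirmatory T2 model, although it is collected on the same scan and used in the ARR, NfL, Gd-lesion and brain-volume models. The possible gain is an interval 0% to 10.9% narrower on the log scale, for an assumed 0% to 30% fall in dispersion, with the plan's rates and 360 patients per arm. It rests on an association that the plan treats as plausible elsewhere but nowhere quantifies. No trial conclusion is likely to depend on it.

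**What to change.** If treatment codes are still blinded, add baseline number of Gd-enhancing T1 lesions as a continuous covariate in SAP 2.6.2.4 and Protocol 9.5.1.1.4, and in the Month 12 to EOS and yearly T2 treatment comparisons (SAP 2.7.2).

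If the codes are open, leave the confirmatory model alone and report the adjusted model as a labelled sensitivity analysis. This matters because the SAP's amendment history already records an addendum made after database lock, and Protocol 8.3 unblinds the treatment codes at lock.

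The NfL-category T2 model in SAP 2.6.2.5 is defined by reference to 2.6.2.4, so it would inherit the covariate. Add a sentence there saying whether the high-versus-low NfL contrast is meant to be adjusted for baseline Gd count.

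The cost is one covariate in text and code, one sentence on NfL, and the loss from this model of any patient without a baseline Gd count, as already happens in the ARR and Gd models. Report how many that is.

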2.6.2.5 Neurofilament light chain (NfL)

The null hypothesis is that there is no difference in NfL between ofatumumab 20 mg sc and teriflunomide 14 mg po by month 3.

- Superiority of ofatumumab 20 mg sc over teriflunomide 14 mg po will be concluded if NfL levels are already lower at month 3 in patients treated with ofatumumab compared with teriflunomide and the observed p-value for the between-treatment comparison is less than the two-sided significance level of 0.05. The multiplicity adjustment explained in [Section 2.5.3](#) applies.
- **Confirmatory analysis of NfL:** The NfL concentration (geometric mean concentration) will be estimated by treatment and time point with 95% confidence intervals using a repeated measures model on the basis of all evaluable log-transformed NfL values (the natural log will be used). The response variable is the log-transformed values of the NfL level as the NfL level is expected to follow log-normal distribution. The exponentiated treatment differences are the geometric mean ratios (GMR) which will be reported by visit window with 95% confidence intervals and p-values. The statistical hypothesis test will be based on the treatment contrast and p-value obtained at month 3. An unstructured covariance matrix will be used. The model will include treatment, region and visit window as factors, and age, number of Gd-enhancing lesions at baseline, baseline T2 lesion volume and the log-transformed NfL baseline concentration as continuous adjustments. The model will also include a treatment-by-timepoint interaction to allow the treatment effect to vary over time. The treatment effect of ofatumumab versus teriflunomide will be visualized in a line plot with 95% confidence intervals.

Supportive analysis: If ofatumumab significantly reduces NfL as compared with teriflunomide, the following additional analyses will be performed. In all patients (FAS), and additionally in the subgroup of newly diagnosed (within 3 years prior to the screening visit) and treatment-

naïve (no prior MS DMT) patients, the hypotheses will be tested that patients with a high (>median) NfL concentration at baseline will experience more new or enlarging T2 lesions, a higher ARR, higher brain volume loss and tend to have a worse disease course on EDSS during the study compared with patients with low (\leq median) NfL concentration at baseline. The median will be estimated from all patients in the combined ASCLEPIOS I and ASCLEPIOS II patients and then applied in all analyses.

- The T2 lesion rate will be estimated using a negative binomial model similar to the one specified in [Section 2.6.2.4](#). In addition, the model will include NfL baseline category and a treatment-by-NfL baseline category interaction. The T2 lesion rate will be estimated by treatment within baseline NfL category. The treatment effect will be expressed as a lesion rate ratio with 95% confidence interval, for low and high baseline NfL category, respectively. From the same model the high vs low NfL contrasts will be estimated with 95% confidence intervals. The statistical hypothesis test with regards to the prognostic value of NfL for new lesion formation will be based on the high vs low baseline NfL category contrast in the teriflunomide group.
- The ARR will be estimated using a negative binomial model similar to the primary model specified in [Section 2.5.2](#). In addition, the model will include NfL baseline category and a treatment-by-NfL baseline category interaction. The ARR will be estimated by treatment within baseline NfL category. The treatment effect will be expressed as an ARR-ratio with 95% confidence interval, for low and high baseline NfL category, respectively. From the same model the high vs low NfL contrasts will be estimated with 95% confidence intervals. The statistical hypothesis test with regards to the prognostic value of NfL for on-study relapses will be based on the high vs low baseline NfL category contrast in the teriflunomide group.
- The disease course based on EDSS will be analyzed as time to 3mCDW, 6mCDW or 6mCDI using Kaplan-Meier curves and a Cox proportional hazard model based on the combined data from COMB157G2301 and COMB157G2302. The model will include study as stratum, treatment, region and baseline NfL category as factors and baseline EDSS as a continuous covariate. In addition the model will include a treatment-by-NfL interaction term. The treatment effect will be expressed as hazard ratio with 95% confidence interval, for low and high baseline NfL category, respectively. The statistical hypothesis test of the prognostic value of NfL for disability changes will be based on the main effect of NfL category. It is acknowledged that the study will not be powered to show an effect on disability outcomes in subgroups. Kaplan-Meier curves will be produced with by treatment and NfL high or low category.
- The brain volume loss rate will be estimated using a random coefficient model similar to the one specified in [Section 2.6.2.6](#). In addition, the model will include NfL baseline category and a treatment by time by NfL baseline category interaction as well as the 3 corresponding 2-way interactions. The annual rate of brain volume change will be estimated by treatment within baseline NfL category. The treatment effect will be expressed as a rate-ratio with 95% confidence interval, for low and high baseline NfL category, respectively. From the same model the high vs low NfL contrasts will be estimated with 95% confidence intervals. The statistical hypothesis test with regards to the prognostic value of

NfL for on-study brain volume loss will be based on the high vs low baseline NfL category contrast in the teriflunomide group.

- The benefit/risk profile of ofatumumab in the subgroup of newly diagnosed, treatment-naïve patients with high NfL will be compared to the overall trial results based on the above described efficacy analyses. The safety profile in the subgroup of newly diagnosed, treatment-naïve patients with high NfL will be compared to the overall trial population by summarizing adverse events by treatment side-by-side for the subgroup and the overall trial by SOC and PT as well as by predefined adverse events as defined in the latest version of case retrieval sheet (eCRS) at the time of analysis implementation (i.e., study database lock).

